5.5 Withdrawal of Subjects and Discontinuation of Study

Lack of response within the context of this study is defined as not achieving at least a 20% improvement in either or both TJC and SJC, compared to Baseline, on 2 consecutive visits. This evaluation begins at Week 32; therefore, Week 36 is the first possible time point a subject might be discontinued for lack of response. From Week 36 onward, study subjects will continue to be evaluated for lack of response on two consecutive visits. Discontinued subjects will be followed through the remainder of the study.

A subject may voluntarily withdraw or be withdrawn from the study or study treatment at any time for reasons including, but not limited to, the following:

- Clinically significant abnormal laboratory result(s) or AEs, which rule out continuation of the study drug, as determined by the Investigator or the AbbVie Therapeutic Area Medical Director (TA MD) (as applicable).
- The Investigator believes withdrawal from the study treatment or study is in the best interest of the subject.

- The subject requests withdrawal from the study treatment or study.
- Eligibility criteria violation(s) are noted after the subject started study drug, if continuation of the study drug would place the subject at risk as determined by the AbbVie TA MD, after consultation with the investigator.
- Subject needs to initiate prohibited medication(s) or dosages, and continuation of the study drug would place the subject at risk as determined by the AbbVie TA MD.
- The subject becomes pregnant while on study drug.
- Subject is non-compliant with TB prophylaxis (if applicable) or develops active TB at any time during the study (see Operations Manual, Section 3.12).
- Subject is diagnosed with a malignancy (Exception: localized non-melanoma skin cancer or carcinoma in-situ of the cervix, where continuation of the subject is at the discretion of the investigator).
- Subject is significantly non-compliant with study procedures which would put the subject at risk for continued participation in the trial as determined by the Investigator or AbbVie TA MD.
- Occurrence of following hepatic test abnormalities that is confirmed on a separate sample following a repeated blood draw:
 - ALT or AST $> 8 \times$ Upper Limit of Normal (ULN);
 - ALT or AST $> 5 \times$ ULN for more than 2 weeks;
 - ALT or AST $> 3 \times$ ULN and (Total Bilirubin $> 2 \times$ ULN or international normalized ratio [INR] > 1.5);

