For EAER calculation, the numerator will be the total number of AEs reported for the event (i.e., a subject can contribute more than one event to the numerator) and the denominator will be the total exposure time among subjects under the treatment group. The number of AEs reported (numerator), the total number of years of study drug exposure (denominator, calculated as total number of days exposed to study drug (i.e., last dose date – first dose date + 140 days) for all treated subjects divided by 365.25), and the exposure-adjusted AE event rate per 100 patient-years calculated as $(\text{[numerator (number of AEs)/denominator]}) \cdot 100$ will be presented for each treatment group.

All continuous laboratory parameters and vital signs variables at each visit will be summarized by actual treatment group sequence defined as follows.

1. Placebo → Risankizumab 150 mg
2. Risankizumab 150 mg → Risankizumab 150 mg

Frequency tables and listings of subjects meeting criteria for potentially clinically significant vital sign values and for potentially clinically significant laboratory values will be provided for Any Risankizumab group by actual treatment received at the time of event. Missing safety data will not be imputed.

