9.2 Adverse Events

A treatment-emergent Adverse Event (TEAE) is defined as an adverse event with an onset date that is after the first dose of study drug, and no more than 140 days after the last dose of study drug.

Adverse events (AEs) will be summarized and presented using primary MedDRA System Organ Classes (SOCs) and preferred terms (PTs) according to the version of the MedDRA coding dictionary used for the study at the time of database lock. The actual version of the MedDRA coding dictionary used will be noted in the AE tables and in the clinical study report. Specific adverse events will be counted once for each subject for calculating percentages, unless stated otherwise. In addition, if the same adverse event occurs

multiple times within a subject, the highest severity and level of relationship to investigational product will be reported.

9.2.1 Analysis of Adverse Events for Period 1

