9.2.1.1 Adverse Event Overview

An overview of AEs will be presented consisting of the number and percentage of subjects experiencing at least one event for each of the following AE categories:

- Any TEAEs
- Any COVID-19 related TEAEs
- Any TEAE related to study drug according to the investigator
- Any serious TEAE
- Any severe TEAE
- Any TEAE leading to discontinuation of study drug
- Any TEAE leading to death
- All deaths
 - COVID-19 related deaths
 - Deaths occurring \leq 140 days after last dose of study drug
 - Deaths occurring $>$ 140 days after last dose of study drug.

Additional AEs may be considered for tabulation/summary based on recommendations from Clinical and Safety as deemed appropriate.

The number and percentage of subjects experiencing at least one event of treatment-emergent AEs will be summarized for each treatment group. The point estimate and 95% CI (using normal approximation and separate group variance) will be provided for the treatment difference in AE percentage between risankizumab group and the placebo group. An overview of the AE of safety interest (ASI) will be provided similarly and the categories of ASI is defined in Section 9.2.1.4. In addition, an overview of AEs per 100 patient-years of study exposure will be presented for the AE categories defined

above. The number of TEAEs reported, the total number of years of study drug exposure, and the TEAE rate per 100 patient-years will be presented.

COVID-19 cases will be identified using relevant terms for COVID-19 search available in MedDRA version 23.0 or higher. All COVID-19 related AEs and COVID-19 related deaths will be summarized in the TEAE Overview table.

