9.2.2.1 Overview of Adverse Events Rates per 100 Patient-Years of Study Drug Exposure

An overview of TEAE per 100 patient-years of study exposure will be presented for the AE categories defined in Section 9.2.1.1.

An overview of ASI per 100 patient-years of study exposure will be presented similarly.

9.2.2.2 Adverse Events Rates per 100 Patient-Years of Study Drug Exposure by SOC and PT

The TEAE rate per 100 patient-years of exposure will be calculated overall, for each SOC and PT, for the same AEs defined in Section 9.2.1 and reported for Any risankizumab 150 mg group.

9.2.2.3 Serious Adverse Events (Including Deaths) and Adverse Events Leading to Study Drug Discontinuation

SAEs (including deaths) and AEs leading to study drug discontinuation will be listed in tables, besides summary by SOC and PT covered in Section 9.2.2.2.

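### The per-100-patient-year tables put deaths over exposure that ends 140 days after the last dose: the later-deaths row has no time at risk, and the all-deaths row is biased in a direction that depends on the analysis

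*SAP*

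**What the plan says.** The overview list in SAP 9.2.1.1 ends with a row for all deaths. Beneath it are COVID-19 deaths, deaths within 140 days of the last dose, and "Deaths occurring $>$ 140 days after last dose of study drug". The section plans counts and percentages for the list, and then adds that "an overview of AEs per 100 patient-years of study exposure will be presented for the AE categories defined" above. It describes the content of that rate table as follows: "The number of TEAEs reported, the total number of years of study drug exposure, and the TEAE rate per 100 patient-years will be presented".

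SAP 9.2.2.1 reuses the list for the long-term analysis: "An overview of TEAE per 100 patient-years of study exposure will be presented for the AE categories defined in Section 9.2.1.1".

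The person-time is defined once, in SAP 9.1 under the long-term analysis, as "last dose date – first dose date + 140 days", summed over treated subjects and converted to years. No truncation at death, withdrawal, Week 24 or data cutoff is stated. SAP 9.2 closes the treatment-emergent window at the same point, "no more than 140 days after the last dose of study drug".

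Follow-up runs past that window. Protocol 5.5 says of subjects taken off drug for lack of response: "Discontinued subjects will be followed through the remainder of the study". Protocol 5.6 asks that anyone who stops drug early keep to the regular visit schedule unless consent is withdrawn.

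**The concern.** A rate is interpretable only if each event in the numerator could have occurred during the time in the denominator. Here the later-deaths row starts where the denominator stops. The all-deaths row adds those later deaths to the in-window ones but counts in-window time only.

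The mismatch also runs the other way. Because the added 140 days are not cut off, a subject whose observation ends sooner than that is credited with time in which no event could have been recorded.

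At stake is the mortality line in the exposure-adjusted tables, above all for the Any Risankizumab group, where SAP 9.2.2 makes exposure-adjusted rates the form of the long-term adverse event analysis. That line would move with how many subjects stop drug and stay in follow-up, and with when the data are cut, even if mortality were constant. It could not safely be set beside a reference rate.

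**Working it through.** The documents give no death rate or patient-year total, so there is no planned figure to reproduce. The check applies the SAP 9.1 formula and compares credited time with observed time.

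**Inputs from the documents.** 420 subjects, 210 per arm; Period 1 doses at Weeks 0, 4 and 16 (days 0, 28 and 112 from first dose); Period 1 safety data to Week 24 (168 days); last dose at Week 208; study length 228 weeks. The timeline is consistent: 208 × 7 + 140 = 1,596 days = 228 weeks.

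**Inputs assumed.** Share d stopping drug early, stopping times uniform over 208 weeks, stoppers followed to Day 1,596, equal mortality on and off drug.

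**1. Later-deaths row.** Each subject contributes zero days beyond day 140 after the last dose. The row has no time at risk in its denominator, whatever is assumed.

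**2. All deaths, long-term final analysis.** A subject who completes dosing is credited 1,596 days and followed 1,596 days, so there is no bias from completers. A subject with a last dose at Week 28 who is followed to the end is credited 196 + 140 = 336 days, leaving 1,260 days (3.45 years) uncounted.

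For the whole trial, with a mean stopping time of 728 days:
- Credited PY = 420 × [(1 − d) × 1,596 + d × (728 + 140)] / 365.25
- Uncounted PY = 420 × d × (1,596 − 728 − 140) / 365.25
- Overstatement = uncounted / credited

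| d | Credited PY | Uncounted PY | All-deaths rate too high by |
|---|---|---|---|
| 10% | 1,751.5 | 83.7 | 4.8% |
| 20% | 1,667.8 | 167.4 | 10.0% |
| 30% | 1,584.1 | 251.1 | 15.9% |
| 40% | 1,500.4 | 334.9 | 22.3% |

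This counts everyone from day 0. For the Any Risankizumab group, the placebo arm starts at Week 24, with 184 weeks (1,288 days) of dosing left. At d = 20%, with stopping uniform over those weeks, that arm is credited 210 × (0.8 × 1,428 + 0.2 × 784) / 365.25 = 747.0 PY, with 210 × 0.2 × 644 / 365.25 = 74.1 PY uncounted. Adding the risankizumab arm (833.9 and 83.7 PY) gives 1,580.9 and 157.8 PY, again 10.0%.

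Timing matters. If everyone who stops has a last dose at Week 28, 5% to 30% stopping gives 4.1% to 31.0%; with a last dose at Week 100, 2.4% to 16.6%.

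**3. All deaths, Period 1, if the same formula is used.** A subject given all three doses is credited 112 + 140 = 252 days against 168 observable, a ratio of 1.5. For 210 such subjects this is 144.9 PY against 96.6 PY. One death reads 0.69 instead of 1.04 per 100 PY, too low by 1 − 168/252 = 33%. Only a single-dose subject has any time past the window before Week 24 (168 − 140 = 28 days). With a share s stopping after one dose and the rest fully dosed, mean credit is 252 − 112s, which falls to 168 only at s = 75%.

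**4. Interim cut-offs.** For an ongoing subject with an assumed mean of 42 days since the last dose, credit exceeds observed time by 140 − 42 = 98 days. The ratio is (364 + 98)/364 = 1.27 at Week 52 and (700 + 98)/700 = 1.14 at Week 100, which lowers the rate.

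**The case against.** The strongest reply is that the rate tables concern treatment-emergent events only. The sentence that follows the list names the number and rate of those events, and 9.2.2.1 is headed as an overview of them. SAP 9.2.2 ties long-term rates to events under risankizumab exposure. On that reading a late death enters no rate, and numerator and denominator agree.

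This weakens the claim that the SAP demands a rate for every death row; it leaves the matter unstated. It does not remove the problem. The list already has a separate row for treatment-emergent events leading to death, so the all-deaths row is something else, and no sentence takes it or its sub-rows out of the rate table. Either these rows get a rate over the wrong time, or the table has rows that cannot be filled.

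Other points on that side stand:
- The 140-day formula appears only under the long-term analysis. Its use in Period 1 rests on the shared term for years of study drug exposure. The other duration definition, in SAP 6.0, adds 84 days; it would credit 112 + 84 = 196 days against 168, a ratio of 1.17.
- Protocol 6.1 collects adverse events to 140 days or 5 half-lives after stopping drug. Visits continue, but complete ascertainment of later deaths is less certain than the full-follow-up assumption implies.
- No death is hidden: the later-deaths row has a count and percentage, and serious events including deaths are listed (SAP 9.2.1.3 and 9.2.2.3).

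A reader might infer that the all-deaths rate is overstated throughout. The documents do not support that: in Period 1 and for ongoing subjects at an interim cut, the same formula pushes the rate down. Nor do they support a fixed percentage error for the later-deaths row, because the SAP does not claim to estimate an off-drug hazard; what can be said is that the row has no matching person-time.

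**Conclusion.** The point holds as a defect of specification. Read literally, the SAP divides deaths beyond 140 days by person-time that excludes their whole risk period, which follows from the text alone. It also gives an all-deaths rate whose bias changes sign between analyses. The 5% to 22% upward bias in the long-term final analysis rests wholly on the assumed stopping pattern, full follow-up and equal mortality. The 33% downward bias in Period 1 is for fully dosed subjects and depends on the 140-day formula applying there. At an interim cut both effects operate, and the net direction depends on the mix of ongoing and stopped subjects. Few deaths are likely, so the effect on the trial's conclusions is limited. It is worth correcting because the rates could not be interpreted as written.

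**What to change.** In SAP 9.2.1.1 and 9.2.2.1:
- Report deaths more than 140 days after the last dose as counts and percentages only.
- Limit the exposure-based death rate to deaths within 140 days of the last dose, with exposure truncated at the earliest of death, end of follow-up, Week 24 (Period 1) or data cutoff.
- If an all-deaths rate is shown, use total time from the first dose of the relevant treatment to death, last study contact or cutoff. For Any Risankizumab, time for subjects who started on placebo then begins at their first risankizumab dose.
- State which person-time definition applies to Period 1.

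The cost is SAP wording and one derived person-time variable. The scheduled visits and the follow-up call should supply the last-contact date, but the documents do not name such a variable, so its availability should be confirmed.

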9.2.1.2 Adverse Events by System Organ Class and Preferred Term

Treatment-emergent adverse events will be summarized by SOC and PT, the following summaries of adverse events will be generated:

- All TEAEs
- Serious TEAEs
- Severe TEAEs
- TEAEs related to study drug according to the investigator
- TEAEs leading to discontinuation of study drug
- TEAE leading to death
- COVID-19 related TEAE

Subjects reporting more than one adverse event for a given MedDRA preferred term will be counted only once for that term (most severe incident for the severity tables and most related incident for the relationship tables). Subjects reporting more than one type of adverse event within a SOC will be counted only once for that SOC. Subjects reporting more than one type of adverse event will be counted only once in the overall total.

TEAEs will also be summarized by relationship to risankizumab 150 mg and placebo as assessed by the investigator as well as by maximum severity, by treatment groups.

The SOCs will be presented in alphabetical order, and the PTs will be presented in alphabetical order within each SOC.

9.2.1.3 Serious Adverse Events (Including Deaths) and Adverse Events Leading to Study Drug Discontinuation

All serious adverse events (SAEs) including deaths and adverse events leading to discontinuation of study drug will be listed in tables, besides summary by SOC and PT covered in Section [9.2.1.2](#).

9.2.1.4 Frequent ($\geq 1\%$) Adverse Events by Preferred Term in Decreasing Frequency

TEAEs occurring for at least 1% of the subjects in any of the treatment arms will be summarized by MedDRA PT in decreasing frequency of Risankizumab treatment group.

Areas of Safety Interest

The Adverse Events of Safety Interest (ASI) categories will be summarized by SOC and PT and will be based on standardized or company MedDRA queries (SMQs or CMQs). ASI are categorized in [Appendix B](#). Adjudicated cardiovascular events will be summarized and presented by treatment group using the CAC adjudicated categories. Serious opportunistic infection excluding tuberculosis and herpes zoster, serious hypersensitivity, serious hepatic events and serious injection site reaction will also be summarized by PT.

In addition, an overview of ASI per 100 patient-years of study exposure will be presented. The number of TEAEs reported, the total number of years of study drug exposure, and the TEAE rate per 100 patient-years will be presented.

Similarly, overview tables for serious ASI in number and percentage as well as in event rate per 100 patient-years will be provided.

Additional AEs may be considered for tabulation/summary based on recommendations from Clinical and Safety teams, as deemed appropriate.

9.2.1.5 Adverse Event by Subgroup

Overview of TEAE and ASI will be assessed by number of prior biologics (0 vs ≥ 1). The number and percentage will be provided for each treatment group. Treatment difference in AE percentage between risankizumab 150 mg and the placebo group will be presented with point estimate and 95% confidence interval.

9.2.2 Analysis of Adverse Events for Long-Term

Long-term adverse event rates will be analyzed using event rates adjusted by cumulative exposure and will be based on the actual treatment received at the time of AE occurrence for the Any risankizumab 150 mg group. This includes AEs occurred under risankizumab 150 mg exposure from subjects starting on risankizumab 150 mg and subjects switching from placebo to risankizumab 150 mg.

9.2.2.1 Overview of Adverse Events Rates per 100 Patient-Years of Study Drug Exposure

An overview of TEAE per 100 patient-years of study exposure will be presented for the AE categories defined in Section 9.2.1.1.

An overview of ASI per 100 patient-years of study exposure will be presented similarly.

9.2.2.2 Adverse Events Rates per 100 Patient-Years of Study Drug Exposure by SOC and PT

The TEAE rate per 100 patient-years of exposure will be calculated overall, for each SOC and PT, for the same AEs defined in Section 9.2.1 and reported for Any risankizumab 150 mg group.

9.2.2.3 Serious Adverse Events (Including Deaths) and Adverse Events Leading to Study Drug Discontinuation

SAEs (including deaths) and AEs leading to study drug discontinuation will be listed in tables, besides summary by SOC and PT covered in Section 9.2.2.2.

9.2.2.4 Areas of Safety Interest Rates per 100 Patient-Years of Study Drug Exposure

The ASI categories will be summarized and presented for the Any risankizumab 150 mg group using SOC and MedDRA PT. The ASI categories will be identified per Standard MedDRA Queries (SMQs)/Company MedDRA Queries (CMQs) in [Appendix B](#). Serious opportunistic infection excluding tuberculosis and herpes zoster, serious hypersensitivity, serious hepatic events and serious injection site reaction will also be summarized by PT for the Any risankizumab 150 mg group.

The ASI rate per 100 patient-years of exposure will be calculated overall, for each SOC and each PT, for each of the category listed in [Appendix B](#).

Similarly, overview table for serious ASI rate per 100 patient-years of exposure will be summarized.

9.3 Analysis of Laboratory Data

Data collected from central and local laboratories, including additional laboratory testing due to an SAE, will be used in all analyses, except for Baseline where SAE-related laboratory assessments on or before the first dose of study drug will be excluded. The clinical laboratory tests defined in the protocol operations manual (e.g., hematology and clinical chemistry) will be summarized.

Each laboratory variable will be summarized for all time points (starting with Baseline) with the number of non-missing observations, mean and standard deviation, median, minimum and maximum. Mean change from baseline to each applicable post-baseline visit will be summarized for selected laboratory variables to compare the treatment difference between risankizumab 150 mg and placebo in Period 1. The number of observations, baseline mean, visit mean as well as the change from baseline mean, standard error, and 95% confidence interval within each treatment group and between treatment groups (risankizumab 150 mg vs. placebo) will be presented.

Changes in laboratory parameters will be tabulated using shift tables by CTCAE criteria v4.03 ([Appendix G](#)).⁴ A shift table from baseline to the worse value (based on CTCAE criteria v 4.03) during treatment will be created. A similar shift table will be provided to summarize shifts from baseline to the final post-baseline value.

Laboratory abnormalities meeting CTCAE criteria grade 3 and higher will be summarized.

Laboratory abnormalities will be evaluated based on Potentially Clinically Significant (PCS) criteria ([Appendix C](#)). For each laboratory PCS criterion, the number and percentage of subjects who have a laboratory value meeting the criteria will be summarized. Listings will be provided to summarize subject-level laboratory data for subjects meeting PCS criteria. A listing of possible Hy's Law cases will be provided.

9.3.1 Variables and Units

All laboratory parameters to be collected in this study are listed below. Laboratory parameters will be reported using the standard international (SI) units.

Table 2. List of Laboratory Variables

Laboratory Variables
Hematology
White Blood Cell (WBC) Count
Red Blood Cell (RBC) Count
Hemoglobin
Hematocrit
Platelets count
Neutrophils
Basophils
Eosinophils
Lymphocytes
Monocytes
Chemistry
Total Bilirubin
Alkaline Phosphatase (ALP)
Aspartate aminotransferase (AST)
Alanine aminotransferase (ALT)
Total Protein
Albumin
Glucose
Triglycerides
Blood Urea Nitrogen (BUN)
Creatinine
Sodium
Potassium
Calcium
Chloride
Bicarbonate
Gamma Glutamyl Transferase (GGT)
Cholesterol
LDL cholesterol
HDL cholesterol

9.3.2 Analysis of Laboratory Data for Period 1

The laboratory data will be summarized by the actual treatment groups: risankizumab 150 mg and placebo group.

